Maternal concern for language delay	Glascoc, 1997		3		Measured by the sum of the two questions included in the PEDS on expressive language and articulation and receptive language: 1. Do you have any concerns about how your child talks and makes speech sounds? (0: No; 1: Yes or a little) 2. Do you have any concerns about how your child understands what you say? (0: No; 1: Yes or a little)
Academic Achievement: Reading					
Reading	McGrew & Woodcock, (2018)	Test-retest reliability ages 5-19: 0.92		6, 8	Woodcock Johnson IV Test of Achievement: Letter-Word Identification. Score range: 0-78; higher scores indicate better performance. Expect higher scores in high- than low-cash gift group.
Reading comprehension	McGrew & Woodcock, (2018)			8	Woodcock Johnson IV Test of Achievement: Passage Comprehension. Score range: 0-52. Expect higher scores in high- than low-cash gift group.

Domains (in gray) and sub-domains	Measure source	Psychometrics	Age preregistered Primary Outcome	Age preregistered Secondary Outcome	Measures and notes (All measures between grey lines measured in the same wave will be subject to multiple testing adjustments)
Academic Achievement: Math					
Math	McGrew & Woodcock, (2018)	Test-retest reliability ages 5–19 = 0.91	6, 8		Woodcock Johnson IV Tests of Achievement: Applied Problems. Score range: 0-56; higher scores indicate better performance. Expect higher scores in high- than low-cash gift group.
Executive Function and Behavioral Regulation					
Executive Function	Diamond & Taylor, 1996; Weiland & Yoshikawa, 2013; Bierman et al., 2008			Originally registered for age 4 and then dropped	Intended to be measured by the pencil tap test. This item was preregistered as an age-4 secondary outcome but was dropped on September 13, 2022, due to evidence of floor effects, and numerous reports from research staff that children were not understanding the instructions.
Executive Function: Minnesota Executive Function Scale	Carlson, 2017; Carlson, & Zelazo 2014	MEFS: validity .92 test-retest .93	4, 6, 8		Measured by the Minnesota Executive Function Scale (MEFS). Score range: 0-100; higher scores indicate better performance. Expect higher scores in high- than low-cash gift group.
Executive Function: NIH Toolbox Flanker Inhibitory Control and Attention Test	Gershon, Wagster, Hendrie, Fox, Cook, & Nowinski, 2013	Test-retest: English 3-15 yo: ICC=0.95; 20-85 yo: ICC=0.83. Spanish 18-85 years old: $\rho=.65$	6, 8		Measured by the NIH Toolbox Flanker task. Score range: 0-30; higher scores indicate better performance. Expect higher scores in high- than low-cash gift group.
Working Memory	Wechsler (2012)		6		Measured by the Wechsler Preschool and Primary Scale of Intelligence (WPPSI) picture memory subtest. Picture Memory score range: 0-35, higher scores indicate better performance. Expect higher scores in high- than low-cash gift group. We pre-register three scores (MEFS, Flanker, Picture Memory), with a plan to do a confirmatory factor analysis and pre-register the impact on the common factor.
Working Memory	Wechsler (2011)		8		Measured by Wechsler Intelligence Scale for Children: 5th Edition (WISC-V) subtest Digit Span. Score Range 0-54. Higher scores indicate better performance. Expect higher scores in high- than low-cash gift group. We will pre-register three scores (MEFS, Flanker, Digit Span), with a plan to do a confirmatory factor analysis and pre-register the impact on the common factor.

Domains (in gray) and sub-domains	Measure source	Psychometrics	Age preregistered Primary Outcome	Age preregistered Secondary Outcome	Measures and notes (All measures between grey lines measured in the same wave will be subject to multiple testing adjustments)
Socio-Emotional Processing					
Social-Emotional Problems	Briggs-Gowan et al., 2004	internal consistency .65-.79 test-retest reliability .87		1, 2	Measured by the Brief Infant–Toddler Social and Emotional Assessment (BITSEA)
Behavior/Emotional Problems	Achenbach et al., 2000	parent report reliability .80	3, 4		Measured by a shortened version of the Child Behavior Checklist measuring the following areas: emotionally reactive, anxious/depressed, attention problems, and aggressive behavior. At age 3, we will estimate the statistical significance of the entire family of related measures in the Child Socio-Emotional Processing outcome cluster measured during the same wave using step-down resampling methods for multiple testing (see statistical analysis plan for more details; Westfall and Young, 1993).
Social-Emotional Behavior	Roggman et al., 2013; Griffen & Friedman, 2007; Belsky, 2007			Originally registered for age 1 but unable to be coded	Measured using NICHD SECCYD parent-child-interaction task coding scheme, with child codes Positive Mood, Negative Mood, Activity Level, Sustained Attention, Positive Engagement at age 1 and agency, negativity, persistence, affection at age 4. (Due to funding limitations, this was not feasible to code, and we have no immediate plans to do so).
Maternal concern for behavioral and social-emotional problems	Glascoe, 1997		3		Measured by the sum of the two questions included in the PEDS on behavior and social-emotional: 1. Do you have any concerns about how your child behaves? (0: No; 1: Yes or a little) 2. Do you have any concerns about how your child gets along with others? (0: No; 1: Yes or a little)
Behavior/Emotional Problems	Achenbach, McConaughy, Ivanova, & Rescorla (2011)	internal consistency .80 - .92, test-retest reliability .81-.85	6, 8		Measured by the maternally-reported Brief Problem Monitor (BPM), assesses attentional, behavioral, and internalizing problems in children. 19 questions and answer choices. Score range: 0-38; higher scores indicate more behavioral problems. Expect lower scores in high- than low-cash gift group. 3 answer choices: 0. Not true as far as you know, 1. Somewhat true, 2. Very true

Domains (in gray) and sub-domains	Measure source	Psychometrics	Age preregistered Primary Outcome	Age preregistered Secondary Outcome	Measures and notes (All measures between grey lines measured in the same wave will be subject to multiple testing adjustments)
Visual Processing and Abstract Spatial Perception					
Visual processing and abstract spatial perception*	Wechsler & Naglieri, 2006	internal consistency .88 test-retest reliability .77	Originally registered for age 4 but not able to be calculated	4, for matrices subtest only	The Wechsler Nonverbal Scale of Ability was originally pre-registered as a Primary Outcome. The IQ score is calculated using two subtests -- Matrices and Recognition -- and we began our fieldwork on July 9, 2022 with both. On the basis of preliminary analysis of the first 71 cases, we discovered that 21% of participants scored at the floor of the Recognition assessment. We therefore dropped the Recognition subtest from our data collection instrument on September 30 2022, precluding us from calculating IQ in subsequent participants. Scores on the Matrices subtest, which measures visual processing and abstract spatial perception (not IQ per se), are now registered as an age-4 secondary outcome.
Fluid Reasoning					
Fluid Reasoning*	Wechsler(2012)		6		Measured by the Wechsler Preschool and Primary Scale of Intelligence (WPPSI) fluid reasoning index, assessed through a composite of two tasks: picture concepts (score range: 0-27; higher scores indicate better performance) and matrix reasoning (score range: 0-26; higher scores indicate better performance). Expect higher scores in high- than low-cash gift group. Note: The Picture Concept subtest had to be dropped on 9/17/2024 due to floor effects.
Perceptual Reasoning					
Perceptual Reasoning*	Wechsler (2011)		8		Measured by the Wechsler Abbreviated Scale of Intelligence--Second Edition (WASI-II) perceptual reasoning index, assessed through a composite of two tasks: block design (score range: up to 8 years old: 0-57; > 9 yo: 0-71; higher scores indicate better performance) and matrix reasoning (up to 8 years old: 0-24; > 9 yo: 0-30; higher scores indicate better performance). Expect higher scores in high- than low-cash gift group.
Pre-Literacy					
Pre-Literacy	Hutton et al., 2019; Hutton et al., 2021			4	Measured by The Reading House

Domains (in gray) and sub-domains	Measure source	Psychometrics	Age preregistered Primary Outcome	Age preregistered Secondary Outcome	Measures and notes (All measures between grey lines measured in the same wave will be subject to multiple testing adjustments)
Resting Brain Function					
Age-1 Resting Brain Function	Tomalski et al., 2013; Otero et al., 2013; Marshall et al., 2004	n/a		1	Measured by low-density mobile electroencephalography at Age 1: we preregistered group differences in theta, alpha, gamma power.
Age-4 Resting Brain Function	Tomalski et al., 2013; Otero et al., 2013; Marshall et al., 2004; Troller-Renfree et al. 2022	n/a	4	4	Measured by high-density in-lab electroencephalography (EEG) Age-4 Primary: Because of limitations in power expected with multiple testing adjustments, we are preregistering a single composite of mid-to-high-frequency whole-brain power summing across alpha, beta, and gamma bands, from 7 to 45 Hz. Age-4 secondary: We hypothesize greater frontal gamma power in the high-cash gift group, and plan to analyze a full model of regions nested within bands, with the plan to report all exploratory outcomes. See attached analysis plan. Note: The original preregistration of EEG data collected when children were 12 months old included hypotheses across multiple frequency bands. Please see the history of preregistrations, including analysis plans.
Age-6 and Age-8 Resting Brain Function	Brito et al., 2020; Brito et al., 2022; Cantiani et al., 2019; Debnath et al., 2020; Gelman et al., 2012; Maguire et al., 2019; Marshall et al., 2004; Rockers et al., 2023, Troller-Renfree et al., 2022; Vanderwert et al., 2010; Vanderwert et al., 2016		6, 8		Measured by high-density in-lab electroencephalography (EEG). Ages 6 and 8 Primary hypothesis: Because of limitations in power expected with multiple testing adjustments, we are preregistering a single composite index of mid-to-high-frequency whole-brain power summed across alpha, beta, and gamma bands (defined as between 7 and 45 Hz). This frequency composite index sums absolute power across all single-Hz interval in the Alpha, Beta, and Gamma bands. We hypothesize that, in the eyes-closed condition, the high-cash gift group will show more power in this composite relative to the low-cash gift group. One-tailed t-tests will be used to test this directional hypothesis. See the Statistical Analysis Plan for additional details.

Domains (in gray) and sub-domains	Measure source	Psychometrics	Age preregistered Primary Outcome	Age preregistered Secondary Outcome	Measures and notes (All measures between grey lines measured in the same wave will be subject to multiple testing adjustments)
	Brito et al., 2020; Brito et al., 2022; Cantiani et al., 2019; Debnath et al., 2020; Gelman et al., 2012; Maguire et al., 2019; Marshall et al., 2004; Rockers et al., 2023, Troller-Renfree et al., 2022; Vanderwert et al., 2010; Vanderwert et al., 2016			6, 8	Age 6 and 8 secondary hypotheses: Our primary hypothesis (detailed above) is based on data gathered in the eyes-closed condition. Corresponding analyses of data from the eyes-open condition will be pre-registered as one of our secondary hypotheses, with the same directional hypotheses as the eyes-closed condition. We expect effects to be smaller in the eyes- open than in the eyes closed condition but do not pre-register hypotheses related to condition by group differences as they will be tested in separate models, are not of immediate theoretical interest, and we are likely to lack the power to detect them. A second set of secondary analyses are based on a different estimation approach. Consistent with another RCT examining brain activity (Debnath et al., 2020; Marshall et al., 2004; Vanderwert et al., 2010, 2016), we will analyze band-specific effects using mixed-effects models, with group as the between-subjects factor and region as within-subjects factor, to examine ITT impacts on each band of relative power in the eyes-closed condition. Our secondary hypotheses for each band are as follows: Theta (high-cash<low-cash), Alpha (high-cash>low-cash), Beta (high-cash>low-cash), and Gamma (high-cash>low-cash). One-tailed t-tests will be used given directional hypotheses. No further multiple-testing adjustments beyond the use of multi-level models will be used (Gelman et al., 2012). See the Statistical Analysis Plan for additional details.
Task-Related Brain Function					
Auditory Discrimination Brain Function*	Choeur et al., 2000; Garcia-Sierra et al., 2011; Kuhl et al., 2005	n/a		4	Measured by mismatch negativity (MMN) ERP with larger differences between standard and deviant stimulus in high-cash gift group compared to the low-cash gift group.

Domains (in gray) and sub-domains	Measure source	Psychometrics	Age preregistered Primary Outcome	Age preregistered Secondary Outcome	Measures and notes (All measures between grey lines measured in the same wave will be subject to multiple testing adjustments)
Health: BMI					
Body Mass Index (BMI)	Kuczmarski, 2000	n/a		4, 6, 8	Measured by CDC BMI percentile scales Age 6/8: We expect to see a reduced percentage of overweight or obese (greater than or equal to 85th percentile) children in the high-cash gift group compared to the low-cash gift group. We will report mean percentile scores of the two groups in descriptive analyses.
Health: Physiological Stress					
Physiological Stress: Hair cortisol	Ursache et al., 2017; Meyer et al., 2014; Davenport et al., 2006	n/a		Originally registered for age 4 but unable to collect	Our original plan was to measure physiological stress using hair cortisol concentration. The first several months of data collection revealed large racial and ethnic differences in willingness to provide a hair sample, due to both cultural and practical reasons. Because of the large amounts of non-random missing data, which would both compromise our statistical power and limit the generalizability of any findings, we dropped hair cortisol from our data collection procedures on October 25, 2022.
Physiological Stress: Nail cortisol	Phillips et al., 2021		6, 8		Child nail samples will be collected to yield a measure of the concentration of cortisol in pg/mg (picograms per milligram). To ensure cortisol levels are within an expected range, values above 500 and equal to or less than 0 will be assigned a missing value. To account for potential outliers, values below 500 will be truncated at the 99th percentile. Cortisol values will be log-transformed. We hypothesize the high-cash gift group will have lower cortisol values when compared to the low-cash gift group. If both fingernail and toenail are collected we will control for whether fingernail or toenail.

Domains (in gray) and sub-domains	Measure source	Psychometrics	Age preregistered Primary Outcome	Age preregistered Secondary Outcome	Measures and notes (All measures between grey lines measured in the same wave will be subject to multiple testing adjustments)
Health: Sleep					
Sleep problems	Yu et al., 2012	reliability .9	3	1, 2	
Measured by PROMIS Sleep Disturbance- Short Form adapted from ECHO; For ages 1 and 2, additive index of the following items with 5-point answer (0: never; 1: almost never; 2: sometimes; 3: almost always, 4: always):
 
 1. difficulty falling asleep 2. sleeping through night (reverse coded) 3. problem with sleep 4. problem sleeping 
Age 3, item 1 was not included in the survey

Health: Other Indicators					
Overall Health, Medical Care, Diagnosis of Condition or Disability	Child's overall health item source: Idler & Benyamini, 1997 Halim et al., 2013	n/a	3	1, 2	
Additive index of the following items*:
 
 1. Child's overall health? (4: excellent, 3: very good, 2: good, 1: fair, or 0: poor) 2. About how many times in the last year did you take child to a doctor because [he/she] was sick? 0-1 times, 2-5 times, 6+ 3. About how many times in the last year did you take child to a doctor because [he/she] was hurt or injured? 4. Did you ever have to take child to the Emergency Room because [he/she] was sick, hurt or injured? (Y/N) 5. How many times ER? 6. Has child been diagnosed with any health condition or disability since birth? (Y/N) 
*factor analysis of items will be conducted to scale the index

Overall Health	Child's overall health item source: Idler & Benyamini, 1997	n/a		4, 6, 8	
Additive index of the following two items (reverse score 1, then add 1 and 2):
 
 1. Child's overall health? 5 answer choices: excellent, very good, good, fair, or poor. Score range: 1-5; higher scores indicate better health. Expect higher scores in high- than low-cash gift group. 2. About how many times in the last year was child sick? 4 answer categories: 0-1 times, 2-3 times, 4-6 times, 7+. Score range: 1-4; higher scores indicate increased occurrences of illness. Expect lower scores in high- than low-cash gift group.

Domains (in gray) and sub-domains	Measure source	Psychometrics	Age preregistered Primary Outcome	Age preregistered Secondary Outcome	Measures and notes (All measures between grey lines measured in the same wave will be subject to multiple testing adjustments)
Diagnosis of Health Condition					
Diagnosis of Health Condition	BFY PIs			6, 8	Has child been diagnosed with any chronic health condition? Yes/No. If yes, asthma and/or something else? We will estimate whether there are group differences, but do not formulate a directional hypothesis, because of two offsetting possibilities: i) the high-cash gift group may have better access to services, which may lead to higher rates of diagnosis and/or ii) the cash gifts may lead to fewer chronic health conditions.
Diagnosis of Developmental Condition					
Diagnosis of Developmental Condition	Study PIs	n/a		4, 6, 8	Dichotomous measure 1:yes 0:no, constructed from the questionnaire categories: Diagnosis of Dev. Condition: speech delay, autism, ADHD, something else (this Q is part of Health Qs) We will estimate whether there are group differences, but do not formulate a directional hypothesis, because of two offsetting possibilities: i) the high-cash gift group may have better access to services, which may lead to higher rates of diagnosis and/or ii) the cash gifts may lead to fewer developmental conditions
Special Services (IEP)	PSID, 2021			6, 8	Maternal report of whether the child has an IEP or receives special educational services using questions adapted from the School Enrollment and Expectations section of the PSID Child Development Supplement. 1: yes; 0: no We will estimate whether there are group differences, but do not formulate a directional hypothesis, because of two offsetting possibilities: i) the high-cash gift group may have better access to services, which may lead to higher rates of diagnosis and receipt of special education and/or ii) the cash gifts may lead to higher school achievement and therefore lower need for special education and individual education plans.

Domains (in gray) and sub-domains	Measure source	Psychometrics	Age preregistered Primary Outcome	Age preregistered Secondary Outcome	Measures and notes (All measures between grey lines measured in the same wave will be subject to multiple testing adjustments)
Child Epigenetic Pace of Aging					
Methylation pace of aging	Belsky et al., 2015; Belsky et al., 2020; Belsky et al., 2022; Higgins-Chen et al., 2022; Levine et al., 2018, Lu et al., 2019	n/a		4	Methylation pace of aging was developed from DNA-methylation analysis of Pace of Aging in the Dunedin Study birth cohort. Pace of Aging is a composite phenotype derived from analysis of longitudinal change in 18 biomarkers of organ-system integrity. In contrast, so-called epigenetic clocks are trained on chronological age. Increments of methylation pace of aging correspond to “years” of physiological change occurring per 12-months of chronological time. The second iteration (DunedinPACE) takes into account an additional measurement occasion (collected 20 years after inclusion) and only includes the most reliable DNA methylation probes, i.e. probes with little variation between technical replicates. If a higher quality measure of epigenetic aging at the time of analysis becomes available, we we will substitute that instead. OSF preregistration link: https://osf.io/ahv2p/?view_only=

Domains (in gray) and sub-domains	Measure source	Psychometrics	Age preregistered Primary Outcome	Age preregistered Secondary Outcome	Measures and notes (All measures between grey lines measured in the same wave will be subject to multiple testing adjustments)
				6, 8	Expect slower DunedinPACE- pace of aging in high-cash group: Methylation pace of aging was developed from DNA-methylation analysis of Pace of Aging in the Dunedin Study birth cohort. Pace of Aging is a composite phenotype derived from analysis of longitudinal change in 18 biomarkers of organ-system integrity. Increments of methylation pace of aging correspond to “years” of physiological change occurring per 12-months of chronological time. We will also report GrimAge Acceleration, which we consider an exploratory analysis. GrimAge represents a DNA-methylation metric designed to predict morbidity and mortality. Briefly, the initial phase entailed the computation of models incorporating physiological indicators, age, sex, and smoking history, with the objective of optimizing mortality prediction within the Framingham Heart Study Offspring cohort. GrimAge will be based on principal components of DNA-methylation to bolster reliability and residualized for chronological age derived from sample receipt age to reflect accelerated biological age.

Domains (in gray) and sub-domains	Measure source	Psychometrics	Age preregistered Primary Outcome	Age preregistered Secondary Outcome	Measures and notes (All measures between grey lines measured in the same wave will be subject to multiple testing adjustments)
Child DNA Methylation					
DNA methylation	McCartney et al, 2022	n/a		4, 6, 8	Expect higher Epigenetic-g in high-cash group: Salivary DNA-methylation profiles of cognitive functioning, i.e., “Epigenetic-g”, can be computed on the basis of weights from a blood-based epigenome wide association study of general cognitive functions (g) in adults. General cognitive ability was derived from the first unrotated principal component of logical memory, verbal fluency and digit symbol tests, and vocabulary. Epigenetic-g is conceptually distinct from biological aging. If a higher quality measure of epigenetic profile of cognitive functioning becomes available at the time of analysis, we will substitute that instead. OSF preregistration link: https://osf.io/ahv2p/?view_only=
Child Nutrition					
Consumption of healthy foods	Los Angeles County WIC Survey, 2017			2, 6, 8	Additive index of the number of times per day consumed the following items: 1. eat fruits 2. eat vegetables Index score: 1: zero, 2: 1 time, 3: 2 times, 4: 3 times, 5: 4 times, 6: 5 or more times. Score range: 1-12; higher scores indicate more consumption of healthy foods. Age 6/8: Expect higher scores in high- than low-cash gift group.
Consumption of unhealthy foods	Los Angeles County WIC Survey, 2017; Hunsberger et al., 2012			2, 6, 8	Age 2: Additive index of the number of times per day consumed the following items: 1. juice, soda, chocolate milk or other sweet drinks 2. eat sweets Age 6/8: . Additive index of the number of times per day consumed the following items: 1. salty snacks such as potato chips, Doritos, Fritos, tortilla chips; 2. sweets or sweetened foods, such as sweetened cereals, fruit bars, Pop-Tarts, donuts, cookies, or candies 3. drink sweetened beverages such as juice, soda, chocolate milk, or other sweet drinks? Index score: 1. zero, 2. 1 time, 3. 2 times, 4. 3 times, 5. 4 times, 6. 5 or more times. Score range: 1-18; higher scores indicate more consumption of unhealthy foods. Expect lower scores in high- than low-cash gift group.

Domains (in gray) and sub-domains	Measure source	Psychometrics	Age preregistered Primary Outcome	Age preregistered Secondary Outcome	Measures and notes (All measures between grey lines measured in the same wave will be subject to multiple testing adjustments)
Any Maternal Concern for Developmental Delay					
Parents' Evaluation of Developmental Status (PEDS)	Glascoe, 1997			3	Measured by the total score across categories of components of the PEDS, which includes 10 survey items.
Total "predictive concerns" in the PEDS	Glascoe, 1997			3	Measured by the total number of maternal-reported concerns that are "predictive of developmental delay" in the PEDS
School Achievement					
Retention	PSID, 2021			6, 8	Maternal report of whether the child has repeated a grade, adapted from the School Enrollment and Expectations section of the PSID Child Development Supplement. Item: Has child ever been held back a grade? (no/yes) Expect fewer retentions in high cash group.
School Behavior					
Suspensions	SIPP, 2023			6, 8	Maternal report of the number of school suspensions, adapted from the Survey of Income and Program Participation. Item: Has child ever been suspended or expelled from school? (no/yes) Expect fewer suspensions in high cash group.
Child engagement in school	Ehrle & Moore, 1999	Cronbach's alpha=.76		6, 8	Maternal report of child's engagement in school using an item adapted from the Survey of Income and Program Participation. "How often would you say that (CHILD) cares about doing well in school"? 4 answer choices: 1. none of the time; 2. some of the time, 3. most of the time; 4. all of the time. Score range: 1-4; higher scores indicate more engagement in school. Expect more engagement in high cash group.
Attendance	BFY PIs			8	During the last 12 months, how many times has (CHILD) been absent? Answer is estimated number of days. Expect fewer absences in high cash group.

Domains (in gray) and sub-domains	Measure source	Psychometrics	Age preregistered Primary Outcome	Age preregistered Secondary Outcome	Measures and notes (All measures between grey lines measured in the same wave will be subject to multiple testing adjustments)
School Quality					
School Quality	Stanford data matched to name of school and city/district			8	Gathered from school names and city/district. We expect an increase in school quality for the high cash group. The measure we select will be a function of what data will be available at the time of Age 8 wave.

Notes. Previous versions of this table specified that "All measures between grey lines will be subject to multiple testing adjustments". This is now changed to be "All measures between grey lines measured *in the same wave* will be subject to multiple testing adjustments".

The previous version of this table referred to "waves" of data collection. For clarity, we have replaced "wave" with "age", with both referring to the age of the baby at planned data collection. Assessment target time is around the child's birthday for each wave, i.e. 12 months, 24 months, 36, months, 48 months, 72 months, and 96 months.

Minor, non-substantive changes may be made to the wording of specific items across data collection years.

Due to COVID-19, the age 3 data collection wave is in the form of a phone survey. Thus, sub-domains that were supposed to be measured in-person at ages 2 or age 3 were postponed to age 4. These domains include: epigenetic age, DNA methylation, BMI, physiological stress, self-regulation, executive function, social-emotional behavior, IQ; resting brain function, auditory discrimination brain function. The sub-domain of child vocalizations was not measured in-person at age 2 (due to COVID-19) and is not being measured at later ages, so it is removed from the pre-registration table.

*Indicates that the sub-domain was called something different in previous versions of this table. The changes are listed below:

- Previously "Communicative Development (Vocabulary)"; presently "Vocabulary".
- Previously "Intelligence"; then "IQ". Presently re-named to domain tested (not IQ per se)
- Previously "Language Related Brain Function"; presently "Auditory Discrimination Brain Function".

Language Development	
Language Milestones	Squires, J., Bricker, D. D., & Twombly, E. (2009). Ages & stages questionnaires . Baltimore, MD: Paul H. Brookes.
Language Processing	Golinkoff, R. M., De Villiers, J. G., Hirsh-Pasek, K., Iglesias, A., Wilson, M. S., Morini, G., & Brezack, N. (2017). User's Manual for the Quick Interactive Language Screener (QUILS): A Measure of Vocabulary, Syntax, and Language Acquisition Skills in Young Children . Paul H. Brookes Publishing Company

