NCT03593356 July 3, 2025

**Household Income and Child Development in the First Years of Life (Baby's First Years)
Statistical Analysis Plans for Phase 1 and Phase 2**

Our Analysis Plan for Phase 1 (dated December 13, 2022) covers hypotheses for data proposed to be collected in our age 4 follow-up. (Analytic plans for hypotheses for data collected in our ages 1, 2 and 3 follow-ups are available through the “Record History” link on the study’s clinicaltrials.gov page.)

Our Phase 2 Analysis Plan (dated June 29, 2024) covers hypotheses for data proposed to be collected in our ages 6 and 8 follow-ups.

This document begins with the December 13, 2022 Phase 1 Plan, followed by the June 29, 2024 Phase 2 Plan. An appendix to this document includes summary charts of all hypotheses and their associated measures for data collected at ages 1, 2, 3, 4, 6, and 8. Child-related hypotheses and measures are listed in Table 9; maternal- and family-related hypotheses and measures are listed in Table 10.

As described in addenda to the Phase 1 and Phase 2 plans, we made two changes to our list of control variables on July 3, 2025. Specifically, in the revised plan’s analyses of age 4, 6 and 8 preregistered child and maternal outcomes, we added to our list of controls i) the child’s age at the time of the assessment and ii) a dummy-variable indicator for the interviewer or of the staff member administering the assessments.

Analysis Plan for Phase 1

Baby's First Years Phase 1: Summary, Pre-registered Hypotheses, Analysis Strategies

December 13, 2022

Project Summary

In the Baby's First Years (BFY) study, one thousand infants born to mothers with incomes falling below the federal poverty threshold in four metropolitan areas in the United States were assigned at random within each of the metropolitan areas to one of two cash gift conditions. The sites are: New York City, the greater New Orleans metropolitan area, the greater Omaha metropolitan area, and the Twin Cities. IRB and recruiting issues led to a distribution of the 1,000 mothers across sites of 121 in one site (the Twin Cities), 295 in two of the other sites (New Orleans and Omaha) and 289 in New York. (We have also randomly sampled 80 of the participating families in the Twin Cities and New Orleans to participate in an in-depth qualitative study, but do not elaborate on those plans in this document.)

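### The age-6 primary Fluid Reasoning outcome is still defined by two subtests, but one was dropped on 9/17/2024, so it cannot be computed as registered for children assessed after that date

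*SAP*

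**What the plan says.** In SAP Appendix Table 9 the Fluid Reasoning row shows age 6 in the primary column and nothing in the secondary column. The measure is the WPPSI "fluid reasoning index, assessed through a composite of two tasks: picture concepts" (range 0-27) and matrix reasoning (range 0-26). The cell ends with: "Note: The Picture Concept subtest had to be dropped on 9/17/2024 due to floor effects".

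Nothing further is said about how the outcome is scored after that date, which children are analysed, or whether it stays primary. The notes under the table, the Phase 2 plan text and the July 3, 2025 addendum are all silent. The addendum changes only the control variables.

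The row directly above (Visual Processing and Abstract Spatial Perception, age 4) describes the same kind of event. An IQ score was to be formed from Matrices and Recognition. Recognition was dropped on September 30, 2022 for floor effects, "precluding us from calculating IQ in subsequent participants". The primary entry was marked as not able to be calculated, the sub-domain was renamed, and the Matrices scores "are now registered as an age-4 secondary outcome".

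**The concern.** A primary outcome needs one definition that can be applied to every child in the analysis set. Here the row keeps a two-subtest index while recording that one subtest stopped part-way. At least three readings remain open:

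- (a) the two-subtest index, in children who have both subtests;
- (b) matrix reasoning alone, in all children;
- (c) whatever subtests each child has, which mixes a two-task and a one-task score according to test date.

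These differ in sample, construct and power. The Phase 2 plan tests its primary hypotheses one-tailed, and Fluid Reasoning is the only measure under its domain heading, so it receives no multiplicity adjustment. If the definition is chosen after data collection has begun, preregistration no longer fixes what this test is. Multiple imputation does not fill the gap. The Phase 2 Attrition section offers it as a sensitivity check, and here it would be imputing a subtest abandoned for floor effects.

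**Working it through.** **1. The plan's own power figure.** Inputs are from the Phase 2 Statistical power section: N = 800 split 40/60 (320 high-cash, 480 low-cash), 80% power, alpha .05. With SD = 1,

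MDE = (z_alpha + z_.80) × sqrt(1/480 + 1/320), where the square root is 0.0722.

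- One-tailed: (1.645 + 0.842) × 0.0722 = .179, against the stated .18.
- Two-tailed: (1.960 + 0.842) × 0.0722 = .202, against the stated .20.

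Both reproduce.

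**2. When age-6 testing could have started.** No start date or count is given. The dates that bear on it are:

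- Recruitment began about April-May 2018 (SAP, Pre-registered Hypotheses) and the age-6 target is 72 months (notes to Table 9). The first children therefore reached the target about April-May 2024.
- The SAP's opening text says: "Our Phase 2 Analysis Plan (dated June 29, 2024) covers hypotheses for data proposed to be collected". The Phase 2 plan adds that updates are registered ahead of each wave. Taken literally, testing began no earlier than June 29, 2024, which is 80 days before the drop.
- The protocol (Research Design) planned recruitment and each annual collection to be spread evenly over 12 months. I assume the same for age 6.

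**3. Share tested before 9/17/2024, and what remains detectable under reading (a).** Share = days from start to 9/17/2024, divided by 365. n = share × 800. One-tailed MDE = 2.486 × sqrt(1/(.24n)), because a 40/60 split gives 1/(.6n) + 1/(.4n) = 1/(.24n).

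| Assumed start | Days | Share | n with both subtests | MDE (SD) | Power at .18 SD |
|---|---|---|---|---|---|
| April 1, 2024 | 169 | 46% | 370 | .26 | 52% |
| May 1, 2024 | 139 | 38% | 305 | .29 | 46% |
| June 29, 2024 | 80 | 22% | 175 | .38 | 32% |
| July 9, 2024 | 70 | 19% | 153 | .41 | 29% |
| Count equal to the age-4 cases | n/a | 9% | 71 | .60 | 18% |

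The July 9 start mirrors the age-4 wave, where "we began our fieldwork on July 9, 2022 with both". The last row borrows the age-4 count, where the floor effect was found "On the basis of preliminary analysis of the first 71 cases" (71/800 = 8.9%).

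**4. Sensitivity to wave length.** The pre-drop share reaches one half only if the wave lasted no more than 2 × 169 = 338 days (about 11 months) from April 1, or 2 × 80 = 160 days (about 5 months) from June 29.

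**5. Under reading (b).** With matrix reasoning scored for everyone, N stays near 800 and the detectable effect near .18 SD. The table does not register that outcome.

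**The case against.** The strongest reply is that the note leaves exactly one task, so the intended score is obviously matrix reasoning alone. Table 10 records other lost components in the same brief way: economic-stress item 9 at age 4, play groups at age 3, and age-1 indices said to have one item fewer. This makes it unlikely that the sponsor means to restrict the primary to early-tested children, so reading (a) should not be presented as the plan's intention. But those are mostly whole-wave omissions from additive survey indices. They do not settle a mid-wave drop from a two-subtest Wechsler index, and at age 4 the sponsor treated that very situation as making the index incalculable.

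Three stronger readings are tempting, and the documents do not support them.

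- *That the documents show most children lack the index.* They do not. This is an inference from dates plus an assumed even 12-month wave.
- *That the treatment comparison is biased.* Assignment was randomised within site and the cut-off is a calendar date that applies to both arms. It does not by itself distort the contrast.
- *That the age-4 precedent requires demotion to secondary.* At age 4 the registered construct was IQ, which Matrices alone does not measure. At age 6 the construct is fluid reasoning, and matrix reasoning is one of its two named tasks. Keeping the single subtest as primary is defensible if it is stated.

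It is also fair that the drop and its reason are dated and disclosed, and that age 6 has several other child primaries whose definitions are unaffected.

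**Conclusion.** The point holds. The age-6 Fluid Reasoning primary, as defined in the current table, cannot be computed for children assessed after 9/17/2024, and the July 2025 revision, about nine and a half months later, left this unresolved. That conclusion rests on the table alone.

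The size rests on assumptions. With an even 12-month wave starting between April 1 and July 9, 2024, 19-46% of 800 children would have both subtests, or about 9% if the number matched the 71 age-4 cases. Under reading (a) the one-tailed detectable effect would be about .26-.60 SD instead of .18 SD. The post-drop group is a majority in every scenario considered, but a much earlier start or a much shorter wave would change that. The harm is lost precision and a construct left open to choice after data collection began.

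**What to change.** Edit the Fluid Reasoning row before any group comparison is run:

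- Define the age-6 outcome as the Matrix Reasoning score (0-26) for all children, tested before or after 9/17/2024.
- Rename it so that it is no longer called an index.
- State that Picture Concepts scores collected before the drop are excluded from the confirmatory analysis.
- State whether the single-subtest score remains primary or becomes secondary, as age-4 Matrices did. Either status is defensible.
- Report the age-6 fieldwork start date and the number of children assessed before the drop, which would replace the assumed shares above.

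The cost is one table edit and a narrower construct than the original composite. In return N stays near 800 and the stated .18 SD detectable effect continues to apply.
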